2.2 Study Design/Type

Schedule of Procedures

Safety Assessments	Screening (-72 hrs)	Day 1 (± 1 day)	Day 3 (± 1 day)	Day 7 (± 3 days)	Day 14 (± 3 days)	Day 28 (± 4 days)	Day 42 (± 2 days)	Day 56 ⁶ (± 2 days)
Inclusion/Exclusion Criteria	X	X						
Physical Examination	X			X	X ⁵	X	X	X
Medical/Surgical History	X		X	X	X	X	X	X
Nutritional Assessment	X				X ⁵		X	X
AUDIT and NIAAA Questionnaires	X							
Timeline Followback Questionnaire	X					X	X	X
Vital Signs	X		X		X	X	X	X
Serial Vital Signs		X		X	X ⁵			
Serum Chemistry ^A	X	X	X	X	X	X	X	X
Coagulation ^A	X	X	X	X	X	X	X	X
Hematology ^A	X	X	X	X	X	X	X	X
Serum pregnancy test	X							
Urine pregnancy test		X		X	X ⁵			
Lipid profile, CRP, SAA1, total protein, albumin ^A	X			X	X ⁵	X		
Calculate MELD Score	X	X	X	X	X	X	X	X
Calculate Lille Score				X				
Calculate Maddrey Score	X							
Urinalysis ¹	X							
ECG ²	X			X	X ⁵	X		
Chest X-ray ³	X							
Adverse Events		X	X	X	X	X	X	X
Concomitant Medications	X	X	X	X	X	X	X	X
Study Drug Dosing		X		X	X ⁵			
Pharmacokinetic Sample Collection ⁷		X	X	X	X	X	X	
Immunogenicity Testing ⁸	X				X	X	X	
Biomarkers(blood and urine)	X ⁷			X	X	X	X	X
Confirmation that patient is abstinent from alcohol		X	X	X	X	X	X	X

1. Urinalysis results can be used for Screening if tested within 7 days.
2. ECG results can be used for Screening if tested within 7 days.
3. Chest X-ray results can be used for Screening if tested within 30 days.
4. Day 1, Day 7 and Day 14 labs and testing must be completed prior to dosing.
5. These tests/procedures will occur only on Day 14 if the patient is receiving a 3rd dose at that visit.
6. Day 56 will only occur if the patient received a 3rd dose on Day 14.
7. Biomarkers are optional at Screening.

^AClinical Laboratory Tests

Hematology	Coagulation	Serum Chemistry		Urinalysis	Other
		Liver Function Tests	Other Chemistry		
Complete Blood Count with differential, Platelet count, MCV	PT, INR	AST, ALT, Total Bilirubin, Direct Bilirubin	Sodium, Potassium, Chloride, Bicarbonate, Calcium, Magnesium, Phosphate, Creatinine, BUN, Glucose, Total protein, Albumin, Lipid profile, CRP, SAA1	Specific gravity, pH, Blood, Protein, Glucose, Ketones	β-HCG serum pregnancy test Urine pregnancy test

Blood will be collected for PK sampling per the schedule below:

⁸Pharmacokinetic Sampling Schedule

Study Visit Day					Study Visit Day +0*	Study Visit Day +2*	Study Visit Day +3*	Study Visit Day +4*
					24 hrs	48 hrs	72 hrs	96 hrs
	Pre-dose	30 mins (±5 mins)	1 hr (±10 mins)	8 hr (±30 mins)				
Day 1	X	X	X	X			X	
Day 7	X	X	X	X	X	X	X	X
Follow-Up Visit Day								
Day 14		X						
Day 28		X						
Day 42		X						

* +/- 2 hour window for PK points > 8 hours after dosing

CONFIDENTIAL

This material is the property of the Mayo Clinic. Do not disclose or use except as authorized.

⁹Immunogenicity Sampling Schedule

Dosing Day			
Baseline	Day 14	Day 28	Day 42
X	X	X	X

2.3 Primary Study Endpoints/Secondary Endpoints

Primary:

- Absence of unexpected serious adverse events.

Secondary:

- Pharmacokinetics (PK) and pharmacodynamics (PD) of F-652 in patients with alcoholic hepatitis.

Efficacy Signal endpoints:

- Decrease in MELD score, Lille score, triglyceride, CRP, AST, ALT and SAA1

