1.5 Risks/Benefits

1. Beneficial Findings:

Animal studies have demonstrated that treatment with F-652 reduces ALT/AST levels in serum and TG in liver. Treatment with IL-22 adenovirus also reduces serum ALT and liver/serum TG levels. Activation of pSTAT3 was seen at 1 hr and was undetectable at 3 hrs. IL-22 induced ALT/AST/TG decreases, however, are not seen in STAT3 (hep-/-) mice. IL-22R1 expression was up-regulated in hepatocytes of alcoholic patients and ethanol-fed mice.

2. Potential Risks:

a. Overdose risk

There has been limited human experience with F-652, either at potential clinical doses or with overdose. Treatment of overdose with F-652 should consist of general supportive measures. If the symptom or sign is judged as a severe disease or disorder, treatment will be administered as per standard of care. There is no known specific antidote for overdose with F-652.

b. Warnings, precautions

There are dose-dependent increases in C reactive protein (CRP) and fibrinogen (FIB) following IV dosing with higher doses of F-652 (30 and 45 µg/kg), commencing at 12-24 hours post-dose. FIB reaches a peak at 96-120 hours post-dose; CRP may reach a peak at 48-72 hours post-dose, returning to normal 2 weeks later.

c. Hypersensitivity

The risk of hypersensitivity reactions to F-652 is unknown. If a significant hypersensitivity reaction occurs, no further doses of F-652 will be administered to that patient and appropriate treatment initiated.

d. Laboratory abnormalities

Increased serum CRP and FIB levels may be observed; these increases will be documented.

e. Local reactions at the injection site

Local injection site reactions such as erythema, dry skin and nummular eczema have occurred after the investigational product was administrated by subcutaneous injection. These changes were seen following intravenous administration at the highest dose (45 ug/kg). Local reactions generally occurred 10 to 17 days after administration of F-652, are usually were mild to moderate. Some subjects required treatment with Elocon (mometasone furoate) 0.1% cream, a moderate to strong topical corticosteroid for their skin reactions.

f. Drug interaction

The potential for drug-drug interactions with F-652 is not known.

g. Pregnancy

Adequate contraceptive methods should be used during treatment with F-652.

h. Geriatric use

There has been no geriatric experience to date.

Since no clinical data is available for F-652; any related SAE will be considered as unexpected.

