1.9 Power Calculation

As the primary outcome is observational, we have powered this study based upon the efficacy outcome, which is defined as a biochemical signal for success if AST/ALT is reduced by at least 30% on treatment. With no treatment, approximately 15-20% of patients reach this outcome following study drug treatment. We anticipate that a minimum of 50% will achieve this outcome. Using a conservative 2-sided assessment of superiority (50% with outcome vs. 20%), we will require 22 subjects to reach 80% statistical power.

For our efficacy outcome of AST/ALT, our primary analysis will assess a binary outcome of at least 30% reduction when on treatment. We will evaluate this with a 95% confidence interval of the percentage of subjects who have at least 30% reduction in AST/ALT on treatment, using an exact binary confidence interval. As a secondary analysis, we will use

CONFIDENTIAL

This material is the property of the Mayo Clinic. Do not disclose or use except as authorized.

robust linear regression with the change in AST/ALT at follow-up as compared to baseline as the outcome variable and baseline AST/ALT as the predictor. We will pair this analysis with a Bland-Altman plot. The goal of the secondary analysis is to assess the degree to which the reduction in AST/ALT attributable to treatment changes according to the subject's baseline AST/ALT. We will use 2-sides 5% type I error rate throughout.

2 *Study Objectives*

Primary:

- Assess the safety and tolerability and find the MTD of F-652 in patients with alcoholic hepatitis as determined by:
 - a. Absence of unexpected serious adverse events and,
 - b. Absence of worsening of alcoholic hepatitis (as determined by increase in MELD score > 5) up to Day 56 following administration of first dose of study drug.

Secondary:

- Determine the pharmacokinetics (PK) and pharmacodynamics (PD) of F-652 in patients with alcoholic hepatitis.

Additional:

- Assess the efficacy signal of F-652 in patients with alcoholic hepatitis as determined by:
 - a. Clinical: improvement in clinical status
 - b. Biochemical: Improvement in liver biochemistry, MELD and Lille scores at days 7, 28, 42 and 56
 - c. Biomarkers of IL 22 activity (CRP, SAA, triglycerides)

2.1 **Trial Design:**

The following study evaluations will be performed during the course of the Screening period (Day -3 to Day 0):

- Signed informed consent

CONFIDENTIAL

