4.3 Treatment Regimen

F-652 will be administered by slow intravenous infusion over approximately 100 minutes. The study medication is reconstituted as per the protocol in 100 ml of 5% dextrose in water. To monitor, as well as prevent hypersensitivity reactions, the infusion rate will be as follows:

1. 10 ml/hr for 15 minutes
2. 20 ml/hr for 15 minutes
3. 40 ml/hr for 15 minutes
4. 80 ml/hr for 15 minutes
5. 100 ml/hr until infusion complete

That is, the total infusion will be over approximately 100 minutes. Patients will be monitored for 3 hours post-infusion with blood pressure and heart rate monitoring every 30 minutes.

CONFIDENTIAL

This material is the property of the Mayo Clinic. Do not disclose or use except as authorized.

Patients will receive two separate IV infusions separated by 6-10 days (i.e. one infusion on Day 1 and a repeat infusion approximately one week later depending on outpatient scheduling). After information is received regarding the primary end point (safety) at the first dose (10ug/kg), and the 10ug/kg dose determined to be safe, the 2nd cohort of patient will be administered the 30ug/kg dose. Further escalation will follow this scheme. If evaluations demonstrate safety and efficacy signals, patients in the final dose escalation cohort will receive a third dose of the study drug at the maximum tolerated dose on Day 14.

Medications allowed: Corticosteroids, pentoxifylline, antibiotics, acamprosate, and Baclofen, as well as any other medication deemed to be essential for the treatment of the patient will be allowed.

Prohibited medications: Biological agents and any other concomitant investigational agents.

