5.2 Method and Timing

1. MELD score will be calculated at each visit.
2. Lille score will be calculated on Day 7.

CONFIDENTIAL

This material is the property of the Mayo Clinic. Do not disclose or use except as authorized.

3. Triglycerides, CRP and SAA1 will be collected at Screening, Day 7, Day 14 (if dosed) and Day 28.
4. AST and ALT will be collected at Screening, Day 3, Day 7, Day 14, Day 28, Day 35, Day 42 and Day 56 (if applicable).
5. Adverse events will be evaluated at each study visit per the Schedule of Procedures by the study coordinator and reviewed by the investigator

6 *Assessment of Safety*

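### A fall in CRP is listed as an efficacy signal, although the protocol says the two higher doses raise CRP and the Day 7 and Day 14 samples fall within that rise

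*Combined protocol and SAP*

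**What the plan says.** Section 2.3 gives one line of efficacy signal endpoints, all with the same direction: "Decrease in MELD score, Lille score, triglyceride, CRP, AST, ALT and SAA1". Section 5.1 lists the same variables as efficacy parameters but speaks only of change.

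Section 1.5 describes what the drug does to CRP: "There are dose-dependent increases in C reactive protein (CRP) and fibrinogen (FIB) following IV dosing with higher doses of F-652". It names 30 and 45 µg/kg, puts the onset at 12-24 hours, and adds "CRP may reach a peak at 48-72 hours post-dose, returning to normal 2 weeks later". Under laboratory abnormalities it repeats the expectation: "Increased serum CRP and FIB levels may be observed; these increases will be documented".

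Section 2 (Study Objectives) places under the efficacy signal objective "Biomarkers of IL 22 activity (CRP, SAA, triglycerides"), without a direction. Section 2.3 separately makes pharmacodynamics a secondary endpoint.

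On timing, Section 5.2 states "Triglycerides, CRP and SAA1 will be collected at Screening, Day 7, Day 14 (if dosed) and Day 28". A note to the schedule in Section 2.2 requires that "Day 1, Day 7 and Day 14 labs and testing must be completed prior to dosing".

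Section 7.1 analyses CRP and SAA1 with linear mixed-effect models, on the pattern of the AST/ALT analysis. That pattern has dose level, baseline value and other baseline characteristics as covariates and a random intercept. No visit term, dose-by-visit term or separate direction is given for CRP.

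**The concern.** The same marker is an expected drug-induced rise in Section 1.5 and an efficacy signal that must fall in Section 2.3. If CRP is measured while the drug is still raising it, the two statements pull in opposite directions. The conflict is worst at the doses where the drug is most active.

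What is at stake is how a dose comparison is read. A higher CRP at 30 or 45 µg/kg than at 10 µg/kg could be taken as weaker efficacy when it only shows that the drug is acting. Conversely, a real anti-inflammatory fall at a later visit could be cancelled by the early rise when visits are averaged. With cohorts of three and no control arm, such a misreading would be hard to detect afterwards.

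**Working it through.** The plan gives no figure on this point to reproduce. The check is whether the CRP samples fall inside the course that Section 1.5 describes.

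**Inputs**
- Course of the CRP rise (Section 1.5): onset 12-24 hours, peak 48-72 hours, normal two weeks later.
- Sampling days (Section 5.2): Screening, Day 7, Day 14 in third-dose patients only, Day 28.
- Dosing-day samples are taken before the dose (Section 2.2), so the Day 7 sample reflects dose 1 and the Day 14 sample reflects dose 2.
- Visit windows (Section 2.2): Day 1 ± 1, Day 7 ± 3, Day 14 ± 3, Day 28 ± 4.
- Dose spacing: "Patients will receive two separate IV infusions separated by 6-10 days" (Section 4.3). The third dose is 7 ± 3 days after the second (Section 1.6).

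**Formula.** Days since last dose = day of sample − day of the most recent earlier dose.

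**Limits from the windows**
- Dose 1 falls on Day 0 to 2. With a gap of at least 6 days, dose 2 is no earlier than 0 + 6 = Day 6, and the visit window makes it no later than Day 10.
- Dose 3 falls on Day 11 to 17.
- The Day 28 visit falls on Day 24 to 32.

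| Sample | Nominal days since last dose | Range with windows |
|---|---|---|
| Day 7 | 7 − 1 = 6 | 6 to 10 (the dosing gap) |
| Day 14, third-dose patients | 14 − 7 = 7 | 4 to 10 (7 ± 3) |
| Day 28, two doses | 28 − 7 = 21 | 24 − 10 = 14 to 32 − 6 = 26 |
| Day 28, three doses | 28 − 14 = 14 | 24 − 17 = 7 to 32 − 11 = 21 |

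**Comparison with the stated course.** Section 1.5 does not say whether the two weeks run from the dose or from the peak. From the dose, the course ends at 14 days. From the peak, it ends at 2 + 14 = 16 to 3 + 14 = 17 days.
- Day 7 and Day 14 lie inside the course on either reading, over their whole ranges. They also lie after the peak, so the rise should be receding.
- Day 28 after three doses is nominally at the edge on the first reading and inside on the second. With windows it can be as early as 7 days.
- Day 28 after two doses is nominally outside on both readings. The lower end of its range, 14 days, is at the edge on the first reading and inside on the second.

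So 1 of 2 post-baseline samples in a two-dose patient falls inside the course. In a three-dose patient it is 2 of 3, with the third at or near the edge.

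**What pooling does.** Take a two-dose patient at a higher dose, give the two visits equal weight, and measure both changes relative to the lowest dose. Let the remaining drug-induced rise at Day 7 be *r* and the true fall at Day 28 be *f*. A dose effect without a visit term then estimates about (*r* − *f*)/2. It is positive whenever *r* exceeds *f*, even though CRP fell by Day 28, and it understates the fall in every case with *r* > 0. The documents give neither *r* nor *f*, so no numerical bias can be calculated.

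**The case against.** The strongest reply is that the model imposes no direction. The Study Summary makes all tests two-sided, a linear mixed model would report a rise as a rise, and no 30% reduction threshold is set for CRP. On this view the only fault is one word in Section 2.3. Much of this stands: the estimate itself is not forced the wrong way. But the word fixes how the estimate will be read, and with no visit term named, early and late samples are combined into one dose effect.

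A second reply is that the CRP rise may not matter in these patients. The only clinical study described in Section 1.4 gave single doses to healthy male volunteers, the samples come after the peak, the remaining rise at 6-7 days is not quantified, and baseline CRP in alcoholic hepatitis is not given. This also stands. A reader might infer that an active higher dose must score as worse efficacy; the documents show only that it could. The same uncertainty gives no support for fixing a decrease in advance at Day 7 or Day 14.

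A third reply concerns SAA1. A reader might infer that it rises too, because it shares the IL-22 activity label with CRP. The documents do not say so: Section 1.5 reports rises in CRP and fibrinogen only, and the label also covers triglycerides, for which a fall of 30% counts as response. This objection stands in full, and the point is confined to CRP.

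**Conclusion.** Wrong as written, but minor. For CRP, the direction in Section 2.3 contradicts the drug effect in Section 1.5 at Day 7 and Day 14, and possibly at Day 28 after a third dose. The consequence is a dose comparison that could be misread, not a bias of known size or sign.

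A reader might go further and infer that the trial's efficacy conclusion or its dose progression is compromised. The documents do not support that. The sample size (Section 1.9) rests on AST/ALT. The main efficacy endpoint (Section 7.1) and the expansion-cohort response (Section 1.6) rest on AST/ALT or triglycerides. Section 2.4 does tie progression to efficacy signals that it does not define, but Sections 1.6 and 4.3 base cohort escalation on toxicity and safety, and nothing says that CRP enters the decision.

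The verdict assumes that the Section 1.5 course carries over at least in part to these patients and to repeat dosing, that CRP is sampled as in Section 5.2, and that the Section 7.1 model has no visit terms beyond those it names.

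**What to change.** - **Section 2.3:** remove CRP from the decrease list and analyse it under the existing pharmacodynamic secondary endpoint, stating in advance that an early rise is expected at 30 and 45 µg/kg.
- **Section 7.1:** report CRP by visit, with dose-by-visit estimates, instead of one pooled dose effect. In cohorts of three these will be descriptive.
- **Interpretation:** read a fall as a possible anti-inflammatory signal only at Day 28 in two-dose patients. Use actual days since the last dose, because the windows allow as few as 14. With no control arm, such a fall cannot be separated from resolution of the disease.
- **SAA1:** treat it as a two-sided activity marker. Do not prespecify a rise, since the documents state no direction of drug effect.
- **Section 5.1:** no edit on direction is needed; it already refers to change.

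The cost is protocol and analysis-plan wording. Samples, visits and sample size stay the same. The downside is one fewer nominal efficacy signal, or two if SAA1 is moved as well.

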2.4 Trial Treatment

Participants will receive 10 µg/kg, 30 µg/kg or 45 µg/kg of F-652 on Day 1 and Day 7 via slow intravenous infusion. Three patients will receive 10 µg/kg of F-652.

Pharmacokinetic testing will be completed on these subjects. If evaluations demonstrate safety and efficacy signals, the next 3 patients will receive 30 µg/kg. If pharmacokinetic testing demonstrates safety and efficacy signals, the next 3 patients will receive 45 µg/kg. If evaluations demonstrate safety and efficacy signals, patients with a MELD score of 21-28 will receive a third dose of the study drug at the maximum tolerated dose on Day 14.

2.5 Remuneration

Each site will compensate participants for their time, travel and parking. The amount will be determined by the site study team and reflected in the consent form.

2.6 Duration

The screening process will occur in the 72 hrs leading up to Day 1. The dosing phase will occur from Day 1 to Day 14. Follow-up will occur between Day 14 to Day 56. Visit activities are described in the previously mentioned Schedule of Procedures.

CONFIDENTIAL

This material is the property of the Mayo Clinic. Do not disclose or use except as authorized.

2.7 Discontinuation

Discontinuation of the F-652 will occur if a participant experiences a Serious Adverse Event or UPIRTSO AND, in the opinion of the investigator and study adjudicator, is related to the study drug. Patients will be discontinued if grade 3 or higher CTCAE develop that are determined to be possibly or likely attributable to study drug.

2.8 Product Accountability

The study drug product will be manufactured, labeled, and supplied by AAI Pharma Services Corporation on behalf of Generon (Shanghai) Corporation, Ltd. The drug will be managed and accounted for by each site's Research or Clinical Pharmacy.

2.9 Data Identification

During the Screening phase, patients will be identified by a unique screening number and by their initials (first and last). On Day 1, patients will be identified by a unique five-digit patient number and initials. Only qualified patients will be assigned a patient number.

3 *Subject Selection Enrollment and Withdrawal*

3.1 Inclusion Criteria

To participate in this study, patients must meet **all** of the following criteria:

1. Able to provide written informed consent (either from patient or patient's legally acceptable representative)
2. Male or female patients 21 years of age or older
3. Patients with alcoholic hepatitis defined as:
 - a. History of heavy alcohol abuse use: >40 g/day in females and >60 g/day in males for a minimum period of 6 months
 - b. Consumed alcohol within 6 weeks of entry into the study
 - c. Serum bilirubin > 3mg/dL AND AST >ALT, but less than 500 U/L
 - d. MELD score between 11-28
 - e. Liver biopsy will be carried out to confirm diagnosis in all patients except those who meet criteria a-c and in whom other causes of liver disease have been excluded (viral, drug, autoimmune etc).
4. Women of child-bearing potential must utilize appropriate birth control.

***Patients on steroids and/or pentoxifylline will not be excluded from the study.**

3.2 Exclusion Criteria

1. Other or concomitant cause of liver disease as a result of:
 - a. Autoimmune liver disease

CONFIDENTIAL

This material is the property of the Mayo Clinic. Do not disclose or use except as authorized.

- b. Wilson disease
- c. Vascular liver disease
- d. Drug induced liver disease

Note: Concurrent viral hepatitis is not excluded.

- 2. Co-infection with human immunodeficiency virus (HIV)
- 3. Any active malignancies other than curatively treated skin cancer (basal cell or squamous cell carcinomas) or any other malignancy diagnosed within the last five years.
- 4. Active tuberculosis on chest x-ray at study entry
- 5. Significant systemic or major illness other than liver disease, including coronary artery disease, cerebrovascular disease, pulmonary disease, renal failure, serious psychiatric disease, that, in the opinion of the Investigator would preclude the patient from participating in and completing the study
- 6. Patients requiring the use of vasopressors or inotropic support
- 7. Liver biopsy, if carried out, showing findings not compatible with alcoholic hepatitis
- 8. Any patient that has received any investigational drug or device within 30 days of dosing or who is scheduled to receive another investigational drug or device in the course of the study

Note: Investigational drug includes any drug that is used off-label.

- 9. If female, known pregnancy, or has a positive urine or serum pregnancy test, or lactating/breastfeeding
- 10. Serum creatinine >2.5 mg/dL

